2.4 Treatments (study treatment, rescue medication, concomitant therapies, compliance)

2.4.1 Study treatment / compliance

Duration of exposure, actual cumulative dose, dose intensity (DI) and relative dose intensity (RDI) will be summarized for PDR001. Duration of exposure will be categorized into time intervals; frequency counts and percentages will be presented for the number(%) of subjects in each interval. The number (%) of subjects who have dose reductions or interruptions, and the reasons, will be summarized.

Subject level listings of all doses administered on treatment along with dose change reasons will be produced.

The safety set will be used for all summaries and listings of study treatment.

Duration of exposure to study treatment

Duration of exposure to study treatment is considered by taking into account the duration of exposure to PDR001:

Duration of exposure to study treatment (days) = (last date of exposure to study treatment) – (date of first administration of study treatment) + 1.

The last date of exposure to study treatment is the planned end date of the last cycle in which the last non-zero dose of PDR001 was last administered (i.e last date of administration + 27 day). If the patient died or was lost to follow-up before the derived last date, the last date of exposure is the date of death or the date of last contact, respectively. If the derived last date of exposure goes beyond the data cutoff date, it should be truncated to the date of data cutoff.

Summary of duration of exposure of PDR001 will include categorical summaries based on 28 days interval and using descriptive statistics (mean, standard deviation etc).

Cumulative dose

Cumulative dose of a study treatment is defined as the total dose given during the study treatment exposure and will be summarized for PDR001.

The **planned cumulative dose** for PDR001 refers to the total planned dose as per the protocol up to the last date of the administration.

The **actual cumulative dose** refers to the total actual dose administered, over the duration for which the subject is on the study treatment as documented in the Dose Administration eCRF.

The actual cumulative dose will be defined based on the days when the subject is assumed to have taken a non-zero dose during dosing periods.

For patients who did not take any drug the cumulative dose is by definition equal to zero.

Dose intensity and relative dose intensity

Dose intensity (DI) for patients with non-zero duration of exposure is defined as follows:

$DI \text{ (mg / week)} = \text{Actual Cumulative dose (mg / week)} / \text{Duration of exposure to study treatment (mg / week)}$.

For patients who did not take any drug the DI is by definition equal to zero.

Planned dose intensity (PDI) is defined as follows:

$PDI \text{ (mg / week)} = \text{Planned Cumulative dose (mg / week)} / \text{Duration of exposure (mg / week)}$.

Relative dose intensity (RDI) is defined as follows:

$RDI = DI \text{ (mg / week)} / PDI \text{ (mg / week)}$.

Dose reductions, interruptions or permanent discontinuations

The number of subjects who have dose reductions, permanent discontinuations, administration stopped/paused during the infusion or interruptions, and the reasons, will be summarized.

‘Dose interrupted’, ‘Was drug administration stopped or paused’ and ‘Dose permanently discontinued’ fields from the Dosage Administration CRF pages (DAR) will be used to determine the dose reductions, dose interruptions, administration stopped/paused and permanent discontinuations, respectively.

The corresponding fields ‘Reason for dose change/dose interrupted’, ‘Reason for administration stopped or paused’ and ‘Reason for permanent discontinuation’ will be used to summarize the reasons.

A dose change is either ‘change in prescribed dose level’ or ‘dosing error’ where actual dose administered/total daily dose is different from the prescribed dose.

For the purpose of summarizing interruptions and reasons, in case multiple entries for interruption that are entered on consecutive dose administrations with different reasons will be counted as separate interruptions. However, if the reason is the same in this mentioned multiple entries on consecutive dose administrations, then it will be counted as one interruption.

Reduction: A dose change where the prescribed dose level is lower than the previous prescribed dose level, where the regimen schedule is modified (less frequent administration of drug compared to previous regimen) or where the actual dose administered/total daily dose is lower than the calculated dose amount based on the prescribed dose. Therefore any dose change to correct a dosing error will not be considered a dose reduction. Only dose change is collected in the CRF, number of reductions will be derived programmatically based on the change and the direction of the change.

Treatment beyond RECIST1.1 progression

The number of patients who continue treatment beyond RECIST1.1 progression according to BIRC assessment will be summarized. It includes all patients who received at least one dose of PDR001 (including incomplete infusion) after BIRC RECIST1.1 progression.

2.4.2 Prior, concomitant and post therapies

The number and percentage of patients who received any prior anti-neoplastic medications, prior anti-neoplastic radiotherapy or prior anti-neoplastic surgery will be summarized for all

patients. Prior anti-neoplastic medications will be summarized by therapy type (e.g. chemotherapy, hormonal therapy, immune-oncology therapy etc.), setting (e.g. adjuvant, metastatic, etc.) and also by lowest ATC class and preferred term. Summaries will include total number of regimens, best response and time from last treatment to progression for the last therapy. The medication therapy type of any combination therapy will be classified based on the following order: immune-oncology therapy, chemotherapy, biologic therapy (other than immune-oncologic therapy), targeted therapy, hormonal therapy. For example, a combination therapy of chemotherapy and hormonal therapy will be classified as 'chemotherapy'. For radiotherapy, time since last radiotherapy, locations and setting of last therapy will be summarized. For prior surgery, time since last surgery, procedure and residual disease of last therapy will be summarized.

Separate listings will be produced for prior anti-neoplastic medications, radiotherapy, and surgery.

Anti-neoplastic medications will be coded using the WHO Drug Dictionary (WHO-DD); anti-neoplastic surgery will be coded using MedDRA. Details regarding MedDRA and WHO-DD version will be included in the footnote in the tables/listings.

The above analyses will be performed using the FAS.

Post treatment anti-cancer therapy

Anti-neoplastic therapies since discontinuation of study treatment will be listed and summarized by ATC class and preferred term, by means of frequency counts and percentages using FAS.

Concomitant medications

Concomitant therapy is defined as all interventions (therapeutic treatments and procedures) other than the study treatment administered to a patient coinciding with the study treatment period. Concomitant therapy include medications (other than study drugs) starting on or after the start date of study treatment or medications starting prior to the start date of study treatment and continuing after the start date of study treatment.

Concomitant medications will be coded using the World Health Organization (WHO) Drug Reference Listing (DRL) dictionary that employs the WHO Anatomical Therapeutic Chemical (ATC) classification system and summarized by lowest ATC class and preferred term using frequency counts and percentages. Surgical and medical procedures will be coded using MedDRA and summarized by SOC and preferred term. Concomitant medications with immunosuppressive intent will be summarized by lowest ATC class and preferred term using frequency counts and percentages. Concomitant medications with immunosuppressive intent will be summarized by lowest ATC class and preferred term using frequency counts and percentages. These summaries will include:

1. Medications starting on or after the start of study treatment but no later than 30 days after start of last dose of study treatment and
2. Medications starting prior to start of study treatment and continuing after the start of study treatment.

Additional summaries will be provided to report medications starting between 31 days after last dose of study PDR001 and 150 days after last dose of PDR001.

The safety set will be used for all concomitant medication tables.

Duration of exposure to concomitant medication with immunosuppressive intent (days) = (last date of exposure to concomitant medication with immunosuppressive intent) – (date of first administration of concomitant medication with immunosuppressive intent) + 1

Duration of exposure to concomitant medication with immunosuppressive intent will be summarized if relevant. In addition, the duration of exposure for the subset of subjects who experienced events of interest (i.e. AESIs, patients treated with concomitant medication with immunosuppressive intent) may be summarized. Descriptive statistics such as median, min, max will be presented.

Time to initiation of concomitant medication with immunosuppressive intent is the time from start of treatment with PDR001 to first administration of concomitant medication with immunosuppressive intent. Patients who did not receive concomitant medication with immunosuppressive intent will be censored. The censoring date will be the earliest of the following dates:

- death date,
- new anticancer antineoplastic therapy start date,
- end date of on-treatment period,
- data cut-off date,
- withdrawal of informed consent date.

Time to initiation of concomitant medication with immunosuppressive intent will be summarized if relevant. Kaplan-Meier curves will be displayed as well as median and 95% confidence intervals for each treatment arm. In addition, time to occurrence for the subset of subjects who experienced events of interest (i.e. AESIs, patients treated with concomitant medication with immunosuppressive intent) may be summarized. Descriptive statistics such as median, min, max will be presented.

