2.7.1 Secondary endpoints

Disease control rate (DCR)

DCR is defined as the proportion of patients with best overall response of CR, PR or SD according to RECIST 1.1 criteria and as per central review. DCR will be calculated using FAS and based on the BIRC tumor assessments.

Time to response

Time to response (CR or PR) is the time from date of treatment start to first documented response of CR or PR (which must be confirmed subsequently) using BIRC review of tumor assessment data and according to RECIST 1.1. All patients in the FAS will be included in the time to response calculation. Patients who did not achieve a confirmed PR or CR will be censored at:

- the maximum follow-up time (i.e. FPFV - LPLV used for the analysis) for patients who had a PFS event (i.e. either progressed or died due to any cause);
- the last adequate tumor assessment date for all other patients.

Progression-free survival (PFS)

PFS is defined as the time from the date of first dose to the date of the first documented radiological progression or death due to any cause. PFS will be assessed via central review according to RECIST 1.1. PFS will be censored if no PFS event is observed before the analysis cut-off date.

If a patient has not progressed or died at the analysis cut-off date, PFS will be censored at the date of the last adequate tumor evaluation date before the cut-off date. PFS events documented after the initiation of new anti-neoplastic therapy (i.e. RECIST 1.1. documented disease progression or death) will be considered provided tumor assessments continue after initiation of new cancer therapy. Discontinuation due to disease progression (collected on the 'End of treatment' and 'End of post treatment follow up' disposition pages) without supporting objective evidence satisfying progression criteria per RECIST 1.1 will not be considered disease progression for PFS derivation.

Efficacy endpoints according to irRECIST

Immune related overall response rate (irORR) is the proportion of patients with a best overall response of irCR or irPR based on BIRC review of tumor assessment data.

The best immune related overall response for each patient is determined from the sequence of immune related overall responses according to rules described in the irRECIST appendix of the protocol.

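### The Kaplan-Meier curve for first immunosuppressive medication censors death and treatment exit, so 1 minus the curve should not be read as the proportion of patients who start immunosuppression

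*SAP*

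**What the plan says.** SAP 2.4.2 defines a variable that "is the time from start of treatment with PDR001 to first administration of concomitant medication with immunosuppressive intent". For non-recipients it says: "Patients who did not receive concomitant medication with immunosuppressive intent will be censored. The censoring date will be the earliest of the following dates". The list has five dates: death, "new anticancer antineoplastic therapy start date", "end date of on-treatment period", data cut-off and withdrawal of consent.

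On output, the section says "Time to initiation of concomitant medication with immunosuppressive intent will be summarized if relevant", and then "Kaplan-Meier curves will be displayed as well as median and 95% confidence intervals for each treatment arm". It names no cumulative proportion at a fixed time and no test. SAP 5.4.2, the only account of time-to-event methods, describes Kaplan-Meier alone.

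Two other parts of the plan bear on this:

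- **Counts.** The same section states "Concomitant medications with immunosuppressive intent will be summarized by lowest ATC class and preferred term using frequency counts and percentages", with a further summary of medications started from day 31 to day 150 after last dose. SAP 2.8.1 and 2.8.1.1 also tabulate adverse events, and those of special interest, that require immunosuppressive medication.
- **End of the on-treatment period.** SAP 2.1.1 sets it 30 days after the last administration. The footnoted rule in SAP Table 5-2 (section 5.1.2) uses the last treatment date plus 150 days, capped by death, cut-off or consent withdrawal.

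**The concern.** Kaplan-Meier treats a censored patient as still able to have the event later, at the same rate as those who remain at risk. A patient who has died cannot start an immunosuppressant. If the target is initiation while on treatment, a patient past the on-treatment window, or on new therapy, cannot have the event either. Censoring these exits redistributes their weight to patients still on drug. The curve then describes a setting without deaths or stopping.

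The SAP recognises a similar problem for time to response. In section 2.7.1, non-responders are censored at "the maximum follow-up time (i.e. FPFV - LPLV used for the analysis) for patients who had a PFS event", because after that event they can no longer respond. The immunosuppression variable has no such provision.

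Non-informative exit is also doubtful. Protocol 6.3.1.2.1 requires permanent discontinuation after any grade 4 immune-related event, and Protocol 7.1.5 lists adverse events as a reason to stop. Leaving treatment is therefore linked to the toxicity that leads to immunosuppression.

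At stake is how the figure and its median are read. A finite median can appear although far fewer than half of the patients ever start these drugs, and the curve will not agree with the percentages reported beside it.

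**Working it through.** The plan gives no figure for this analysis, so there is none to reproduce. The check compares the two estimators under constant monthly hazards.

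**Formulas.** Let l1 be the hazard of starting immunosuppression and l2 the hazard of a competing exit.

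- Kaplan-Meier complement: 1 − KM(t) = 1 − exp(−l1·t)
- Cumulative incidence: CIF(t) = l1/(l1+l2) × [1 − exp(−(l1+l2)·t)]

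The first is never below the second.

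**Inputs.**

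- Incidence of immunosuppressive use: not in the documents. Assumed 5%, 10%, 20% and 30% at 12 months.
- Median on-treatment time: assumed 2.8, 4, 6 and 12 months. The lowest value is a rough figure from Protocol 1.2.1.2: median exposure of 8.0 weeks in the phase II part of the first-in-human study (other tumours), plus 30 days. That is 56 + 30 = 86 days, and 86/30.4375 = 2.8 months.
- Share of exits that are deaths: 13 of 127 treatment discontinuations in the same study, or 10.2%.

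**Worked case: median 2.8 months, every exit competing.** l2 = ln 2/2.8 = 0.2476. A true 12-month incidence of 10% requires l1 = 0.0287, since 0.0287/0.2763 × [1 − exp(−12 × 0.2763)] ≈ 0.10. Then 1 − KM(12) = 1 − exp(−12 × 0.0287) = 29.1%.

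**Results for a true 12-month incidence of 10%.**

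| Median on-treatment time (months) | 1 − KM, every exit competes | 1 − KM, only death competes |
|---|---|---|
| 2.8 | 29.1% | 11.6% |
| 4 | 22.8% | 11.1% |
| 6 | 18.1% | 10.7% |
| 12 | 13.7% | 10.4% |

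The right-hand column uses a death hazard of l2 × 13/127 and takes the other exits as non-informative. Over incidences of 5% to 30%, the ratio of 1 − KM to the true incidence runs from 1.35 to 3.02 when every exit competes, and from 1.03 to 1.16 when only death does.

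**The median.** Suppose the exit median is 3 months and 25% of patients ever start. Then l2 = ln 2/3 = 0.2310 and l1 = (0.25/0.75) × 0.2310 = 0.0770. At 12 months, CIF = 0.25 × [1 − exp(−12 × 0.3081)] = 24% and 1 − KM = 1 − exp(−0.924) = 60%. The Kaplan-Meier median is ln 2/0.0770 = 9.0 months, although 75% never start. A milder case, with a 5-month exit median and 15% ever starting, gives 12.9% against 25.4%.

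**A different target.** A simulation (400,000 patients per scenario) let immunosuppression start for about 4 months after the on-treatment period, roughly to day 150. With median 2.8 months and l1 = 0.02, 1 − KM(12) is 21.3%. The true incidence is 12.7% if the later hazard equals the on-treatment hazard, 22.9% if it is 3 times as high, and 35.2% if it is 6 times as high. The direction of the error therefore depends on which starts count.

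**The case against.** A reader might infer that the trial will overstate how many patients need immunosuppression. The documents do not support that. That information comes from counts and percentages in SAP 2.4.2, 2.8.1 and 2.8.1.1, none of which uses this censoring rule. It would also go too far to say that the curve fails a stated safety question. The safety endpoint is the frequency and severity of adverse events with other safety data (SAP Table 1-1), and no objective concerns the timing of toxicity management.

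The strongest technical reply is that only death makes the event impossible. A patient who stops PDR001 or starts another therapy can still receive steroids, and the SAP summarises starts to day 150. Censoring at exit could then target an initiation rate while on treatment. For the same reason the comparison with time to response fits only partly. Nor could that convention simply be copied: with staggered entry and censoring at cut-off, holding competing exits at risk without weights is not the same estimator as Aalen-Johansen.

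These points limit the size and the priority. They do not rescue the planned output. The SAP never says that a while-on-treatment rate is meant, and a Kaplan-Meier curve with a median invites reading as a proportion. SAP 2.4.2 ties concomitant therapy to the treatment period, so on-treatment incidence is the natural reading, and under it all three exits compete. The counts are not a full substitute either: they include drugs already ongoing at first dose, and they carry no timing.

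**Conclusion.** The concern holds in a limited form. Read as the proportion of patients who start immunosuppression on treatment, 1 minus the planned curve is biased upward and its median is too early. The direction follows from the estimator. The size does not come from the documents: it rests on constant hazards, assumed use rates, and exit patterns borrowed from another population. The two ranges, 1.03 to 1.16 and 1.35 to 3.02, mark the difference between counting only death as competing and counting every on-treatment exit. A reader might take the larger range as established, but it requires the on-treatment target, which the SAP implies and does not state. If starts up to day 150 were the target, the curve could be too low.

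The analysis is descriptive and conditional, and it drives no decision. This is a low-priority correction to make if the analysis is produced.

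**What to change.** If the analysis is produced, amend SAP 2.4.2 as follows.

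1. State the target. For on-treatment initiation, replace the Kaplan-Meier curve and median with an Aalen-Johansen cumulative incidence. Treat death, end of the on-treatment period and new antineoplastic therapy as competing events, and censor only at data cut-off and consent withdrawal.
2. If initiation up to day 150 is wanted instead, treat death as the competing event and do not censor at the end of the on-treatment period. Say how new therapy is handled, because Protocol Table 7-1 then limits collection to medications for reported suspected adverse events.
3. Report cumulative incidence with 95% confidence intervals at fixed times.
4. Reconcile the end of the on-treatment period between SAP 2.1.1 (30 days) and SAP Table 5-2 (150 days), since it sets the exit date.
5. State how immunosuppressants already ongoing at first dose are handled, and replace the reference to treatment arms, which does not fit a single-arm study.

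The cost is SAP wording and a competing-event code in PROC LIFETEST, which SAP 5.4.2 already uses. No new data are needed for the on-treatment target. The downside is slightly more programming and the loss of a curve that summarises the hazard while on treatment.

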2.5 Analysis of the primary objective

The primary objective is to estimate the antitumor activity of PDR001 as a single agent in well-differentiated NET and poorly-differentiated GEP-NEC groups.

2.5.1 Primary endpoint

ORR is defined as the proportion of patients with best overall response (BOR) of complete response (CR) or partial response (PR) according to RECIST 1.1 (see Appendix 1 of the study protocol). ORR will be calculated within each group based on the FAS using BIRC review of tumor assessment data. Patients with only non-measurable disease at baseline will be part of the analysis and will be included in the numerator only if a complete response was observed. Tumor assessments performed before the start of any further antineoplastic therapy (i.e. any additional secondary antineoplastic therapy or surgery) will be considered in the assessment of BOR. Limited-field palliative radiotherapy administered as concomitant therapy per protocol will not

be considered as new antineoplastic therapy. Localized radiotherapy and treatment with bisphosphonates for pre-existing, painful bone/liver metastases is permitted.

